## 5 INTRODUCTION TO THE CLINICAL INVESTIGATIONAL PLAN

### 5.1 Background

Atrial fibrillation (AF) is among the most prevalent arrhythmias in the world today affecting approximately 1.5-2% of the general population. The age of patients with AF is steadily rising and now averages between 75 and 85 years of age. AF is associated with a five-fold risk of stroke, a three-fold incidence of congestive heart failure, and higher mortality.

Symptoms arise from the rapid, irregular rhythm as well as the loss of cardiac pump function related to uncoordinated atrial contractions. These uncoordinated contractions also allow blood to pool in the atria and may ultimately lead to thromboembolism and stroke.

AF is characterized by a chaotic contraction of the atrium in which an electrocardiogram (ECG) recording is necessary to diagnose the arrhythmia. Any arrhythmia that has the ECG characteristics of AF and lasts sufficiently long for a 12-lead ECG to be recorded, or at least 30 seconds on a rhythm strip, should be considered an AF episode.

The diagnosis requires an ECG or rhythm strip demonstrating: (1) Irregular RR intervals (in the absence of complete AV block), (2) no distinct P waves on the surface ECG, and (3) an atrial cycle length (when visible) that is usually variable and less than 200 milliseconds.

AF can be characterized into four classifications:

- Paroxysmal AF (PAF) is defined as recurrent AF ( $\geq$ two episodes) that terminates spontaneously within seven days.
- Persistent AF is defined as recurrent AF that is sustained for seven days. In addition, patients with continuous AF who undergo cardioversion within seven days should be classified as having paroxysmal AF if the cardioversion is performed within 48 hours of AF onset, and persistent AF if the cardioversion is performed more than 48 hours after AF onset.

---

 Camm AJ, et al. 2012 focused update of the ESC Guidelines for the management of atrial fibrillation: an update of the 2010 ESC Guidelines for the management of atrial fibrillation--developed with the special contribution of the European Heart Rhythm Association. *Europace*, 2012 Oct; 14(10):1385-413

### 3D Mapping

Three-dimensional (3D) electroanatomical contact and noncontact mapping systems have been reported to facilitate ablation of AF by identifying anatomical structures and highlighting the location of ablated sites. This can guide the initial ablation and help identify existing gaps in an incomplete lesion set. Additionally, electromagnetic navigation systems have been shown to substantially reduce the fluoroscopy time required for AF ablation.

### The AcQMap System

The AcQMap™ High Resolution Imaging and Mapping System (AcQMap System) has been designed to provide information on cardiac dipole densities as a function of time and project that information on an image of a cardiac chamber. In this study, the AcQMap System will collect data from the AcQMap 3D Imaging and Mapping Catheter (AcQMap Catheter) to create anatomical reconstructions of the chamber(s) being mapped and to create Dipole Density maps on those reconstructions. These maps will then be used to identify mechanisms of atrial fibrillation, which can be targeted for ablation.

Since it is hypothesized the technology advances of dipole density mapping may better identify and more precisely direct lesion locations during AF ablation, the study is additionally designed to record longer term (six- and twelve-month) data on the effectiveness of the ablation procedure in the treatment of the arrhythmia. An analysis of treatment success (defined as freedom from atrial fibrillation at 6 and 12 months), compared to literature based historical controls, may offer insight regarding the ability of the AcQMap System to effectively and accurately identify appropriate ablation targets. However, since ablation techniques and catheter choices are not controlled during the study, clinical outcomes will not be used to imply the effective creation of lesion sets in the left atrium substrate.

Automatic, instantaneous, and simultaneous 3D display of the left atrial surface with associated charge densities may potentially shorten AF ablation procedure time and provide an intuitive tool to rapidly identify and guide effective treatment. To further assess these potential benefits of the AcQMap System during the study procedures, data will be collected for many other procedural and clinical outcomes.

Data from this study will be combined with a nearly identical pre-market clinical study conducted in Canada and Australia. Data are considered suitable for pooling based on identical patient inclusion and exclusion criteria, procedures, and measurement methods for outcomes data. The patients in the general population of the countries conducting the study have similar demographics. Analysis of primary safety data will be adjudicated by a common, independent CEC. The pooled data will be utilized to statistically assess the safety and performance of the device when used in the ablation treatment of persistent AF.

### **5.2.1 Patient Reported Outcomes (AFEQT)**

The clinical study is designed to include reported changes in a patient's quality of life following an ablation for atrial fibrillation. The Atrial Fibrillation Effect on Quality of Life (AFEQT) Questionnaire is a "validated, comprehensive, disease-specific measure to quantify the impact of AF and its treatment on a full spectrum of a patient's health". By evaluating a subject's perception of their symptoms and functional impairment at pre-procedure and all

---

follow-up visits, the test will measure the impact of rhythm management on their health and wellbeing.

### **5.3 Indication for Use Statement**

The AcQMap™ Imaging and Mapping System is intended for imaging and mapping of cardiac chambers, which will be utilized in the management of cardiac arrhythmias.

### **5.4 Device Description**

#### **5.4.1 General System Description**

The AcQMap™ System is designed to create a 3D image of a heart chamber's endocardial surface in which catheters can be navigated and a chamber-wide electrical activation map can be overlaid for percutaneous procedures. The AcQMap™ System should only be used by physicians thoroughly trained in electrophysiology procedures and trained on the use of the AcQMap™ System

#### **5.4.2 AcQMap System Hardware**

The AcQMap™ System hardware consists of the AcQMap™ Console, AcQMap™ Workstation and the AcQMap AIU/PIU. The AcQMap Console contains all electronics for interfacing with patient-contacting devices such as the AcQMap™ Catheter and the Patient Electrode Kit.

#### **5.4.3 The AcQMap 3D Imaging and Mapping Catheter**

The AcQMap 3D Imaging and Mapping Catheter is a diagnostic, sterile, single-use device that has a polymeric catheter torque shaft, an integral handle and a flexible, metallic deployable/retractable array.

#### **5.4.4 AcQGuide Steerable Sheath**

The AcQGuide Steerable Sheath is a single-use, sterile, delivery sheath consisting of a deflectable shaft with a lumen, integral handle with steering mechanism, hemostasis valve and flush port. The sheath is compatible with other Acutus Medical catheter products. The sheath can be placed within the desired heart chamber thus allowing the AcQMap Catheter to be introduced, deployed and directed within the chamber as needed.

## **6 CLINICAL STUDY**

### **6.1 Clinical Study Objective**

The objective of the clinical study is to evaluate the incidence of device- and procedure-related safety, efficacy, and efficiency (6- and 12-month outcomes) when using the AcQMap as an imaging and mapping system for ablation of persistent atrial fibrillation (AF).

### **6.2 Clinical Study Design**

The clinical study is a prospective, single-arm, multi-center, multi-national, non-randomized, post-market study designed to provide clinical data regarding the use of the AcQMap System during an ablation of persistent atrial fibrillation. In parallel with this clinical study, a second study, identical in design, inclusion/exclusion criteria and reportable outcomes, will be conducted in geographical locations where regulatory approval has not been obtained. The data from these collaborative studies will be pooled for analysis and eventual publication on the use of the AcQMap System for mapping and imaging during ablation of persistent AF.

#### **6.2.1 Primary Measurable Objective**

The primary measurable objective is an analysis of the proportion of subjects who are free from device/procedure related Major Adverse Events (MAEs) that occur within the first 24 hours post-procedure. MAEs include any of the following:

- Death
- Cardiac perforation/tamponade
- Cerebral infarct, transient ischemic attack (TIA), or systemic embolism
- Major bleeding
- Mitral or tricuspid valvular damage
- Other serious adverse device effects (SADEs) adjudicated by an independent Clinical Events Committee (CEC) as “probably related” to the AcQMap System

#### **6.2.2 Secondary Measurable Objectives**

Secondary measurable objectives include the following:

##### Safety Outcome Measure

- Recording and analysis of all identified adverse events (AEs) and adverse device effects (ADEs) through 12 months post-procedure. Events will be adjudicated by an independent Clinical Events Committee (CEC) for severity and relationship to the AcQMap

### Procedure Outcome Measure

- Analysis of the proportion of subjects with acute procedural (ablation) success defined as:
  - Conversion to sinus rhythm (with or without DCCV) within 12 hours of the procedure
  - Procedural conversion to atrial flutter, atrial tachycardia or other organized supraventricular rhythm

### Clinical Outcome Measures

- Analysis at 3, 6, 9, and 12 months post ablation (with a 24 hour continuous ECG monitor) of the proportion of subjects with freedom from documented episodes of AF lasting longer than 30 seconds. Analysis will include:
  - Freedom from AF/AT/AFL without AADs
  - Freedom from AF/AT/AFL with AADs
  - Freedom from AF/AT/AFL with a single procedure
  - Freedom from AF/AT/AFL with multiple procedures

## **6.3 Clinical Study Duration**

Enrollment is anticipated to take approximately six (6) to eight (8) months. Post-procedure follow up will occur at hospital discharge, 1, 3, 6, and 12 months. The total study duration is anticipated to be approximately 18 months.

## **6.4 Clinical Study Sample Size and Clinical Sites**

Up to one hundred and twenty-five (125) patients will be enrolled at up to fifteen (15) clinical sites in Europe. No site may enroll more than 25 patients (20% of the study population).

## **6.5 Clinical Study Enrollment Definitions**

For the purposes of this clinical study, the following definitions regarding the status of a subject will apply:

Screen Failure Subject – Any subject who has not met all of the inclusion and exclusion criteria. This includes a subject who may be excluded based on the results of the pre-procedure TEE. Screen failure subjects should have the screening eCRF completed and the screening data entered in the database.

Enrolled Subject – Any subject who has signed an informed consent form and is deemed study eligible by meeting all of the inclusion and exclusion criteria.

Pre-treatment Subject – Any enrolled subject who has the venous access portion of the ablation procedure initiated. Pre-treatment patients that do not complete the AcQMap procedure will be followed for adverse events through hospital discharge. In addition to the discharge eCRF, a study completion eCRF will be completed. No follow-up beyond the hospital discharge will be required.

Treatment Subject – Any pre-treatment subject who completes the ablation procedure to the point the AcQMap catheter and AcQGuide sheath has been deployed in the left atrium. Treatment subjects will be followed for all study outcome measures for the full duration of the clinical study. The number of treatment subjects will be used for the study sample.

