## 2.2 Analysis Populations

The following analysis populations will be defined for the study:

**Safety Population** – The safety population will include all enrolled subjects who have the venous access portion of the ablation procedure initiated.

**Treatment Population** – The treatment population will include all enrolled subjects who complete a procedure up to the point the AcQMap catheter has completed mapping the atrial anatomy.

The analysis of the primary safety objective of the study will be based on the safety population. The analysis of the secondary safety and effectiveness outcomes will be based on the safety population or the treatment population as indicated in Sections 4 and 5 below.

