#### 4.1.2 Secondary Safety Objectives

The secondary safety analysis measures are defined as follows:

- All adverse events (AEs) reported through 12 months
- 12-lead ECGs and Holter monitor results
- Physical exam findings
- Vital signs

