#### 4.2 Analysis of Safety Objectives

##### 4.2.1 Analysis of Primary Safety Objective

Subjects who remain free from device/procedure related MAEs, as adjudicated by the CEC, that occur within the first twenty-four (24) hours post index procedure will be considered a success with respect to the primary safety objective, and subjects who experience at least one such MAE will be considered a primary safety failure. MAEs that occur during the first 24 hours will be reported and adjudicated by the CEC for any probable relationship to the device and/or procedure.

The analysis of the primary safety objective will be performed on the safety population. The number and proportion of subjects in the safety population who are primary safety successes will be computed, along with a 95% exact binomial (i.e., Clopper-Pearson) confidence interval on the proportion.

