##### 4.2.2 Analysis of Secondary Safety Objectives

With the exception of treatment emergent adverse events (TEAEs), all analysis of secondary safety objectives will be conducted on the treatment population. TEAE analyses will be conducted on the safety population.

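### Subjects who do not complete the AcQMap procedure need not be followed after discharge, yet the SAP keeps them in the 24-hour primary analysis and the 12-month adverse event tables, with no rule for incomplete observation

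*Combined protocol and SAP*

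**What the plan says.** **Follow-up (protocol 6.5).** A pre-treatment subject is one in whom venous access has begun. "Pre-treatment patients that do not complete the AcQMap procedure will be followed for adverse events through hospital discharge", and "No follow-up beyond the hospital discharge will be required". A study completion form then closes the subject out. By contrast, "Treatment subjects will be followed for all study outcome measures for the full duration of the clinical study". The section adds that "The number of treatment subjects will be used for the study sample".

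**Analysis sets (SAP 2.2, 4.2.1, 4.2.2, 4.1.2).** "The safety population will include all enrolled subjects who have the venous access portion of the ablation procedure initiated". On the primary endpoint, "The analysis of the primary safety objective will be performed on the safety population". A subject free of adjudicated, device- or procedure-related MAEs for 24 hours after the index procedure is a success; a subject with at least one is a failure. For adverse events, "TEAE analyses will be conducted on the safety population", and the secondary safety measures in SAP 4.1.2 include "All adverse events (AEs) reported through 12 months".

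**Related rules.**
- The adverse events part of SAP 4.2.2 counts an event as treatment-emergent (TEAE) only if it begins at or after deployment of the AcQMap catheter in the left atrium.
- SAP 2.3 prescribes complete-case analysis, with exceptions only for Holter rhythm and partial dates.
- The statistical summary in the protocol synopsis puts the primary analysis on the treatment population, not the safety population. Protocol 8.2 names no population.
- Protocol 7.4.1 lists the evaluations due before discharge but sets no minimum stay.

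**The concern.** A proportion is interpretable only if everyone in the denominator was observed over the period it describes. Here part of the safety population may be observed for less time than the endpoint covers.

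For the primary endpoint, a subject whose procedure is abandoned and who goes home before 24 hours has no required contact for the rest of the window. A bleed, effusion or embolic event declaring itself in that interval might never be recorded. The MAE-free proportion is the only primary endpoint and the basis of the sample size, and SAP 2.4 lets 24-hour data be used for publications or marketing before all subjects reach that time point.

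In the 12-month adverse event tables the mismatch does not depend on length of stay. These subjects sit in the denominator for a year although only their hospital stay has to be observed.

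**Working it through.** **Inputs from the documents.** N = 125 and an assumed 96.0% MAE-free, so 120 successes and 5 failures; 95% Clopper-Pearson interval; target half-width 3.89% (protocol 8.4, SAP 1.3).

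**Assumptions.** The documents give neither the number k of subjects who do not complete the AcQMap procedure nor their discharge times. I take k = 1, 3, 6 and 13, about 1% to 10% of 125, and suppose the worst case in which none has a known 24-hour outcome. Because protocol 6.5 counts the sample in treatment subjects, k is added to 125. I also assume that the parallel study, whose protocol is not available here, has the same follow-up rule; SAP 1.0 describes its procedures as identical.

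**1. The plan's own figure.** For x successes in n, lower limit = Beta⁻¹(0.025; x, n−x+1) and upper limit = Beta⁻¹(0.975; x+1, n−x). At 120/125 this gives 90.91% to 98.69%, so the half-width is (98.69 − 90.91)/2 = 3.89%. The stated figure reproduces and is not in dispute.

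**2. Primary endpoint under three treatments of the k subjects.** Excluding them gives 120/125 = 96.00% (90.91 to 98.69) for every k.

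| k | Scored as successes, (120+k)/(125+k) | Scored as failures, 120/(125+k) |
|---|---|---|
| 1 | 121/126 = 96.03% (90.98 to 98.70) | 120/126 = 95.24% (89.92 to 98.23) |
| 3 | 123/128 = 96.09% (91.12 to 98.72) | 120/128 = 93.75% (88.06 to 97.26) |
| 6 | 126/131 = 96.18% (91.32 to 98.75) | 120/131 = 91.60% (85.47 to 95.73) |
| 13 | 133/138 = 96.38% (91.75 to 98.81) | 120/138 = 86.96% (80.17 to 92.08) |

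Success scoring instead of exclusion raises the estimate by 0.03 to 0.38 points and the lower limit by 0.07 (90.98 − 90.91) to 0.84 (91.75 − 90.91) points. The failure column is a bound, not an expectation.

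**3. One MAE actually missed.** 1/125 = 0.8 points: 119/125 = 95.2% (89.9 to 98.2) instead of 120/125 = 96.0% (90.9 to 98.7).

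**4. The 12-month tables.** Take a 20% rate among 125 treated subjects, that is 25 subjects, and let the k subjects add to the denominator only: 25/126 = 19.8%, 25/128 = 19.5%, 25/131 = 19.1%, 25/138 = 18.1%.

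**5. Why those k subjects add no events.** There are two causes. Required follow-up stops at discharge. In addition, a subject stopped before deployment never reaches the moment from which TEAEs are counted, so even an access-site complication seen in hospital falls outside the tables. Longer follow-up alone would therefore add nothing to the TEAE numerator.

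**6. If the k subjects fall within the 125.** The synopsis caps enrolment at 125. With k = 13 inside that number, exclusion gives 107/112 = 95.54% against 120/125 = 96.00% when they are scored as successes, a difference of 0.46 points; the 20% rate shows as 0.20 × 112/125 = 17.9%. The picture is much the same.

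**The case against.** The strongest reply is that the primary-endpoint gap may never arise. It needs a subject discharged less than 24 hours after the procedure, and the documents give no discharge times. Protocol 7.4.1 asks for telemetry, a physical and neurological examination, adverse event review and an ECG before discharge, and a qualifying MAE found then already counts as a failure. This stands: the gap is conditional.

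A reader might infer that the plan scores unobserved time as event-free and so always flatters the result. The documents do not go that far. Success scoring is the natural reading of SAP 4.2.1, which takes the proportion over the safety population, but the complete-case rule in SAP 2.3 could be read as dropping such subjects. Where no event was missed, success is also the correct score. The complete-case reading does not rescue the plan, however: an abandoned case with an early MAE would stay as a known failure while one discharged early without an event would be removed, which biases the other way.

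The synopsis is a further defence. On the treatment population, which protocol 6.5 follows in full, the 24-hour gap disappears. So do MAEs in subjects who never enter that population, and SAP 2.2 and 4.2.1 both specify the safety population.

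Existing contacts do not clearly close the gap. The 7-day call in protocol 7.4.2 refers to subjects generally, but protocol 6.5 exempts this group from anything after discharge. The phone contact in protocol 11.5 is for withdrawn subjects, where possible.

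Finally, less follow-up where the device was never deployed can be a reasonable design choice. That is fair, but the analysis sets then have to match it.

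**Conclusion.** The mismatch between required follow-up and analysis population is in the text and should be corrected. For the 12-month tables it holds whatever the length of stay: an assumed 1 to 13 subjects would turn a 20% rate into 19.8% to 18.1%, and the TEAE start point contributes to this alongside the short follow-up. For the primary endpoint it holds only if such subjects leave before 24 hours, and the passages on scoring, missing data and primary population must be reconciled before one can say how they would be counted. The scoring effect is small, 0.03 to 0.38 points under the assumed k, plus about 0.8 points for each MAE actually missed. The documents do not support a claim that the primary result is materially inflated: they say neither how often nor why procedures are abandoned.

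**What to change.** 1. **Protocol 6.5:** extend the existing 7-day phone contact to every safety-population subject, to establish MAE status through 24 hours after the procedure.
2. **SAP 4.2.1:** count a subject as a success only when 24-hour status is known. Report the number unknown, with a sensitivity analysis counting them as failures. State how SAP 2.3 applies to this endpoint, and reconcile the primary population with the synopsis.
3. **SAP 4.2.2:** for the safety population, start adverse event counting at venous access and report those events through the 7-day contact. Report 12-month percentages on the subjects followed for 12 months. For that purpose, reconcile the treatment definition in protocol 6.5 (catheter and sheath deployed) with SAP 2.2 (mapping completed), so that the denominator is the group actually followed.

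The cost is a few phone calls and a few sentences in the protocol and SAP. The MAE-free figure may become slightly less favourable.

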## **6.6 Clinical Study Population**

The patient population will consist of men and women between the ages of 18 – 80 years of age scheduled for an endocardial ablation of persistent atrial fibrillation (AF).

A potential study subject will be eligible for study enrollment only if all of the following inclusion and none of the exclusion criteria apply:

### **6.6.1 Inclusion Criteria**

- IC 1 Male or female between the ages of 18 and 80 years of age
- IC 2 Currently scheduled for an ablation of persistent atrial fibrillation defined as AF lasting at least 7 days but no more than 12 months without electrical or chemical cardioversion
- IC 3 Willingness, ability and commitment to participate in baseline and follow-up evaluations for the full length of the study
- IC 4 Willing and able to give informed consent

